9.6. Data management

Data management (data programming and analysis) will be conducted on secure servers with regular backup provided by HIRA. All statistical analyses will be performed using SAS Enterprise Guide 7.1 (SAS Institute Inc., Cary, NC, USA), provided by HIRA through a virtual access machine.

9.7. Data analysis

Phase I of the study (descriptive)

Main Analysis

PFIZER CONFIDENTIAL

- Descriptive analysis will be conducted separately in two cohorts of non-cancer VTE and cancer VTE patients according to co-presence of active cancer.
- Sociodemographic and clinical characteristics will be summarized with means (standard deviations [STD]) or median (interquartile range [IQR]) for continuous variables and with count (proportions) for categorical variables for the three treatment groups of interest: PAC only (UFH, LMWH, UFH+LMWH), warfarin-based (warfarin, PAC/warfarin) group, NOAC-based (NOAC, PAC/NOAC) group. Analysis of variance, and chi-square test will be conducted for continuous variables, and categorical variables, respectively.
 - In order to distinguish between PAC bridging therapy and PAC treatment, we will apply a time restriction of 2 weeks to PAC bridging therapy.
- Temporal trend in anticoagulation therapy for VTE will be presented between 1 Mar 2013 and 30 Jun 2019. Proportions of the index OACs will be estimated according to calendar year and quarter.
- The number and percentage of patients who discontinue treatment completely, experience treatment interruption and treatment switch during their follow-up will be described by the index anticoagulant treatment received. Results will be limited to the first of each of these events for each patient. For patients experiencing a treatment switch, the new treatment will be described at the time of their first switcher per individual drug.
- The duration of the index treatment by the index anticoagulant treatment received will also be summarized in terms of days using descriptive statistics (mean [STD], median [IQR]).
- The Kaplan-Meier method will be applied to derive the empirical distribution of time to each of the treatment endpoints of interest (e.g., treatment discontinuation or switch); these analyses will be performed per index anticoagulant treatment received and no comparisons will be made. Log-rank test will be conducted at the 3-, and 6 months after treatment initiation to assess statistical significance between the survival curves among three treatment groups of interest. Persistent rate will also be calculated at the same time point.
- In the NOAC-based group, all analyses will be repeated stratified by each individual NOAC class (e.g, apixaban, dabigatran, rivaroxaban, edoxaban) to identify the difference in baseline characteristics and treatment patterns between each NOAC class.
- To identify potential reasons for treatment change, clinical events preceding the first treatment change (major bleeding, thromboembolism diagnosis, complications of VTE, major surgery, active cancer, a new diagnosis of CKD or AKI, a new diagnosis

of liver disease or abnormal liver function) will be measured within 30 days prior to the first date of treatment change. Patients can contribute with multiple events.

- All analyses of treatment patterns will be presented stratified according to the index anticoagulant treatment, and not overall or per drug class.

Phase II of the study (comparative)

Propensity score analysis

- To balance and adjust for any potential differences in baseline sociodemographic and clinical characteristics between treatment groups, propensity score (PS) methods will be implemented.
 - A logistic regression model will be used to estimate the predicted probability (propensity) of initiating each NOAC compared with warfarin given baseline covariates mentioned above. By using the estimated PS, we will apply the PS based on the inverse probability of treatment weights (IPTW), where the treatment group of interest will be given a weight of 1/PS, and the comparator group will be given a weight of 1/(1-PS) [25, 26]. The most extreme 1% of PS values (IPTW with trimming) will be excluded to improve comparability between exposure groups.

Main Analysis

- Sociodemographic and clinical characteristics will be summarized with means (STD) or median (IQR) for continuous variables and with count (proportions) for categorical variables for the two treatment comparisons of: apixaban vs warfarin, rivaroxaban vs warfarin, edoxaban vs. warfarin and dabigatran vs. warfarin (and NOAC vs. NOAC, if scientifically feasible).
 - Differences in baseline covariates between users of different OACs will be assessed using the SD where the absolute SD <0.1 will be considered as well balanced.
- The incidence rate of major bleeding overall and by site will be presented as the total number of events per 1,000 person-years, with its 95% CIs estimated using the Poisson distribution.
- The risk of major bleeding according to the treatment of interest will be investigated in time-to-event analyses using standard Kaplan-Meier methods.
- Cox proportional hazards model will be used to compare the safety outcome between users of different OACs, weighted on the estimated PS according to the IPTW approach.

PFIZER CONFIDENTIAL

- Proportionality assumption will be tested by use of Schoenfeld residuals.

Subgroup Analysis

- The potential heterogeneity of treatment effects in selected subgroups of patients with VTE will be examined for the major bleeding as follows:
 - Aged <65 years vs. aged \geq 65 years
 - Females vs. males
 - Setting of VTE diagnosis (inpatient vs. outpatient)
 - Type of VTE (DVT without PE vs. PE with or without DVT)
 - Major orthopedic surgery-provoked VTE
 - Major orthopedic surgery-provoked VTE is defined as an event preceded by knee arthroplasty, hip arthroplasty, or hip fracture surgery (National Procedure Codes: N0305, N0601, N0611, N0641, N0711, N2070, N0715, N2710, N0731, N0981, N0991, N1711, N3710, N1721, N3720, N1715, N4710, N1725, N4720, N2072, N2077, N2712, N2717, N3712, N3717, N3722, N3727, N4712, N4717, N4722 or N4727) within 3 months period prior to index date
 - With vs. without CKD stage 3 or 4 (N18.3, N18.4)
- P-for-interaction value <0.05 will be used to denote a significant difference between the two groups.

Sensitivity Analysis

- Vary the definition of treatment interruption/discontinuation to 15 and 60 days (allowing for varying non-adherence) to assess the effect this had on study outcomes.
- Four other approaches involving PS will be applied to determine the robustness of our study findings. First, we will vary the extreme value of PS in trimming process (most extreme 5%, and 10% will be excluded). Second, we will include the estimated PS, in addition to other covariates, into our multivariable Cox proportional hazards regression model. Third, we will stratify on the estimated PS in deciles. Lastly, we will apply another weighting approach, standardized mortality ratio weights, with the weights given as follows: 1 for the treatment group of interest and PS/(1 – PS) for the comparator group.[25]

- Exclude patients with a history of bleeding during the 6-month pre-index-date period in Phase II comparative analysis to evaluate the robustness of findings with respect to changes in underlying risk of patients

Detailed methodology for summary and statistical analyses of data collected in this study will be documented in a statistical analysis plan (SAP), which will be dated, filed and maintained by the sponsor. The SAP may modify the plans outlined in the protocol; any major modifications of primary endpoint definitions or their analyses would be reflected in a protocol amendment.

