- Had a record of active cancer, defined as first diagnosis of cancer with V code (a special code applied to patients with confirmed diagnosis of cancer by Korean Ministry of Health and Welfare for reimbursement for 5 years or longer if recurrent/metastatic) within the past 6 months of period prior to index date; or receiving anti-cancer treatment (chemotherapy, radiation therapy, or cancer-related surgery) under cancer diagnosis with V code within the past 6 months period prior to index date

Follow-up

- **Phase I of the study:** Patients will be followed-up from the index date until the earliest of in-hospital death or end of the study period (31 Dec 2019).
- **Phase II of the study:** Patients will be followed-up from the index date until the earliest of outcome occurrence (bleeding event), treatment discontinuation, switch to another anticoagulant, in-hospital death, or end of the study period (31 Dec 2019), where patients will be considered to have discontinued treatment when new prescription is absent within the 30-day grace period after the end of the former prescription.

- **Variables**

Exposure(s)

- Anticoagulant therapy (PAC [LMWH, UFH, others], NOACs [apixaban, dabigatran, rivaroxaban, edoxaban], warfarin).

Outcome(s)

- **Phase I of the study:** sociodemographic and clinical characteristics of patients with VTE, utilization of index anticoagulant treatment, treatment patterns (including treatment interruption, switching, complete discontinuation), overall treatment duration, and clinical events preceding first treatment change
- **Phase II of the study:** Primary or secondary diagnosis with major bleeding (by site: intracranial, gastrointestinal [GI], and other sites) after the index date

Covariate(s)

- Sociodemographics (age, sex) will be assessed on the index date. Clinical characteristics including comorbidities, previous use of medications, and the number of outpatient visits will be assessed within the 6-month period prior to the index date

- **Data sources**

- South Korea's Health Insurance and Review Assessment Service (HIRA) database

- **Study size**

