- Previous use of medications (WHO-ATC code) will be measured within the 6-month period prior to the index date.
- Corticosteroids (H02)
 - Nonsteroidal anti-inflammatory drugs (NSAIDs; M01A)
 - Angiotensin-converting enzyme (ACE) inhibitors (C09A, C09B)
 - Angiotensin II receptor blockers (ARBs; C09C, C09D)

- Antiplatelet agents (aspirin [N02BA01], aspirin/dipyridamole [B01AC30], abciximab [B01AC13], beraprost [B01AC19], cilostazol [B01AC23], clopidogrel [B01AC04], iloprost [B01AC11], indobufen [B01AC10], limaprost [C04AX], ozagrel [R03DX], prasugrel [B01AC22], sarpogrelate [B01AC], ticagrelor [B01AC24], ticlopidine [B01AC05], tirofiban [B01AC17], Treprostinil [B01AC21], triflusal [B01AC18])
 - Azole antifungal agents (fluconazole [J02AC01], itraconazole [J02AC02], voriconazole [J02AC03], posaconazole [J02AC04])
 - β -blockers (C07)
 - Calcium-channel blockers (C08)
 - Selective serotonin reuptake inhibitors (SSRIs; N06AB)
 - Proton pump inhibitors (PPIs; A02BC)
 - Diuretics (C03)
 - Thiazides (C03A)
 - Vasodilators (C01D, C04A)
 - Estrogens (G03C)
 - Cyclooxygenase (COX)-2 inhibitors (M01AH)
- Number of outpatient visits within the 6-month period prior to the index date.

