a. Baseline conditions included: Charlson comorbidity index, HAS-BLED scores, comorbidities (antiphospholipid syndrome, asthma, cancer, chronic obstructive pulmonary disease, chronic kidney disease, chronic liver disease, diabetes mellitus, fracture, heart failure, hyperlipidemia, hypertension, ischemic heart disease, myocardial infarction, stroke, trauma), previous use of medications (corticosteroids, nonsteroidal anti-inflammatory drugs, angiotensin-converting enzyme inhibitors, angiotensin II receptor blockers, antiplatelet agents, azole antifungal agents, β-blockers, calcium-channel blockers, selective serotonin reuptake inhibitors, proton pump inhibitors, diuretics, thiazides, vasodilators, estrogens, cyclooxygenase-2 inhibitors), initial presentation of VTE (DVT, PE, both DVT and PE), number of outpatient visits

b. Earliest of: outcome of interest (major bleeding event), treatment discontinuation, switch to another anticoagulant, in-hospital death, end of the study period (31 Dec 2019)

Note: Dx, diagnosis; NOAC, non-vitamin K antagonist oral anticoagulant; Rx, prescription; VTE, venous thromboembolism; PE, pulmonary embolism

Figure 2. Overall study schematic

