Cancer surgeries	Specified in 'cancer-related surgery' of section 8.3.2
Benign surgeries	R4123-R4129, R4421, R4430, R3975
Cancer-related event (active cancer)	C00-C97 (excluding non-melanoma skin cancer, C44) with V code (V011, V027, V193, V194)
Kidney function change	
Chronic kidney disease	N18, N19
Acute kidney injury	N17
Liver function change	
Liver disease	B15-B19, K70-K77
Abnormal liver function	R94.5, R74.0

- **Phase II of the study**

- Major bleeding will be defined using primary or secondary diagnosis codes according to the ICD-10 diagnostic codes shown in below table and classified by site (intracranial, gastrointestinal [GI], all others).

Major bleeding	ICD-10 diagnosis code	Diagnostic definition
Intracranial hemorrhage	I60, I61, I62, I690, I691, I692, S064, S065, S066, S068	Diagnosis code + admission code + brain CT or MRI code

		* Brain CT or MRI: CT: HA441, HA451, HA461, HA471, HA851 MRI: HE101, HE102, HE135, HE201, HE202, HE235, HE301, HE302, HE401, HE402, HE501, HE502, HE535
GI bleeding	I850, I983, K2211, K226, K228, K250, K252, K254, K256, K260, K262, K264, K266, K270, K272, K274, K276, K280, K282, K284, K286, K290, K3181, K5521, K625, K920, K921, K922	Diagnosis code + admission code
Other bleeding	D62, H448, H3572, H356, H313, H210, H113, H052, H470, H431, I312, N020-N029, N421, N831, N857, N920, N923, N930, N938, N939, M250, R233, R040, R041, R042, R048, R049, T792, T810, N950, R310, R311, R318, R58, T455, Y442, D683	Diagnosis code + admission code

- The earliest date of diagnosis of the major bleeding event after the index date will be defined as the outcome occurrence date.
- Patients will be followed up from the index date to the occurrence of an outcome, treatment discontinuation (30-day grace period), switch to another anticoagulants, in-hospital death, or end of the study period (31 Dec 2019) whichever comes first.

Potential Confounder(s)

- Sociodemographic characteristics such as age, sex, and index year will be assessed at the index date.
- CCI [2] and HAS-BLED [3] scores will be measured within the 6-month period prior to the index date.

List of CCI	Score	ICD-10 codes
Cerebrovascular disease	1	G45, G46, H34, I60-I69
Congestive heart failure	1	I09.9, I11.0, I13.0, I13.2, I25.5, I42.0, I42.5-I42.9, I43, I50, P29.0
Chronic pulmonary disease	1	I27.8, I27.9, J40-J47, J60-J67, J68.4, J70.1, J70.3

Dementia	1	F00–F03, F05.1, G30, G31.1

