Note: PAC, parenteral anticoagulants; IQR, Interquartile range; std, standard deviation

Table 13. Pre- and post-weighted baseline characteristics of patients with venous thromboembolism who newly initiated apixaban and warfarin.

Characteristics	Pre-weighted			Post-weighted		
	Apixaban		Warfarin-based therapy	Apixaban	Warfarin-based therapy	aSD
	N=	(%)	N=	(%)	N=	(%)
Follow-up (days; median, IQR)						
Age (years; mean±std)						
Age group (years; n, %)						
18-40						
40-65						
≥65						
Sex (n, %)						
Male						
Female						
Health insurance type (n, %)						
National health insurance						
Medical aid						
Index year (n, %)						
2012						
2013						
2014						
2015						
2016						
2017						
2018						
2019						
CCI score (mean±std)						
HAS-BLED score (mean±std)						
Comorbidities (n, %)						
Antiphospholipid syndrome						
Asthma						
History of cancer						
COPD						
Chronic kidney disease						
Chronic liver disease						
Diabetes mellitus						
Fracture						

Heart failure
Hyperlipidemia
Hypertension
Ischemic heart disease
Myocardial infarction
Stroke
Trauma
Previous use of
medications (n, %)
Corticosteroids
NSAIDs
ACE inhibitors
Angiotensin II receptor
blockers
Aspirin
 β -blockers
Calcium-channel
blockers
SSRI
Proton pump inhibitors
Diuretics
Thiazides
Vasodilators
Estrogens
Cyclooxygenase-2
inhibitors
Outpatient visits
(mean \pm std)

Note: ACE, angiotensin-converting enzyme; aSD, absolute standardized difference; CCI, Charlson comorbidity index; COPD, chronic obstructive pulmonary disease; IQR, interquartile range; NSAIDs, nonsteroidal anti-inflammatory drugs; PAC, parenteral anticoagulants; SSRI, selective serotonin reuptake inhibitors; std, standard deviation

Table 14. Pre- and post-weighted baseline characteristics of patients with venous thromboembolism who newly initiated rivaroxaban and warfarin.

Characteristics	Pre-weighted			Post-weighted		
	Rivaroxaban	Warfarin-based therapy	aSD	Rivaroxaban	Warfarin-based therapy	aSD
	N= (%)	N= (%)		N= (%)	N= (%)	
Follow-up (days; median, IQR)						
Age (years; mean±std)						
Age group (years; n, %)						
18-40						
40-65						
≥65						
Sex (n, %)						
Male						
Female						
Health insurance type (n, %)						
National health insurance						
Medical aid						
Index year (n, %)						
2012						
2013						
2014						
2015						
2016						
2017						
2018						
2019						
CCI score (mean±std)						
HAS-BLED score (mean±std)						
Comorbidities (n, %)						

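### The covariate lists behind the propensity score contain no inpatient-use variable and do not name health insurance type, so the NOAC-warfarin hazard ratios may carry residual confounding that data already held could reduce.

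*Protocol*

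**What the plan says.** Protocol 9.7, repeated in SAP 10, fits a logistic model to "estimate the predicted probability (propensity) of initiating each NOAC compared with warfarin given baseline covariates mentioned above". Neither document gives a separate list of model terms, so the confounder lists in Protocol 9.3 and SAP 8.4 define the model. They contain:

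- age, sex and index year, introduced by an open-ended sentence: "Sociodemographic characteristics such as age, sex, and index year will be assessed at the index date";
- Charlson and HAS-BLED scores;
- initial VTE presentation;
- 15 comorbidities and 15 medication classes;
- one measure of healthcare use: "Number of outpatient visits within the 6-month period prior to the index date".

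The note to the study schematic in SAP 8.2 ends the same way: "initial presentation of VTE (DVT, PE, both DVT and PE), number of outpatient visits". The Protocol Abstract is shorter still: "Sociodemographics (age, sex) will be assessed on the index date".

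SAP Table 13 is titled "Pre- and post-weighted baseline characteristics of patients with venous thromboembolism who newly initiated apixaban and warfarin". It and Tables 14-16 each have a row beginning "Health insurance type (n", under pre- and post-weighting columns with an absolute standardised difference (aSD). The balance rule is that differences are "assessed using the SD where the absolute SD <0.1 will be considered as well balanced". No step is given for a covariate that misses it. Prior admissions appear in no list and no table.

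**The concern.** Insurance type is shown as a characteristic whose balance will be inspected after weighting, but no text places it in the model that produces the weights. Two programmers could fit different primary models, one with it and one without, and both could claim to follow the plan.

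Prior admission matters because of how the outcome is defined. Intracranial, gastrointestinal and other bleeding all require an admission code, and secondary diagnoses count. As the definition reads, a patient admitted for another reason who also has a coded bleed is an event. A tendency to be admitted is therefore a plausible predictor of a recorded event. If it is also related to the choice between warfarin and a NOAC, given the listed covariates, it confounds the comparison. Outpatient visits capture a different kind of contact.

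No planned analysis closes the gap. Heavier trimming, the score as a regression covariate, deciles of the score and standardised mortality ratio weights all start from the same covariate lists. The E-value analysis in Protocol 9.9 is worded for apixaban only, is missing from SAP 10 and Table 20, and in any case does not replace adjustment for something that can be measured.

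**Working it through.** **Where each variable appears**

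| Variable | Protocol 9.3 / SAP 8.4 lists | SAP Tables 13-16 | Evidence that the data are held |
|---|---|---|---|
| Health insurance type | Not named; sociodemographic sentence is open-ended | Yes, with aSD | The SAP tabulates it |
| Prior admissions | Absent | Absent | Care setting is recorded (Protocol 9.4); admission codes define the outcome |
| Outpatient visits | Named | Yes | Already used |

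The insurance categories also differ between tables. Tables 1-4 have National health insurance, Medical aid and Veterans; Tables 13-16 have only the first two.

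**The plan's own figure.** The plan gives no figure for confounding. Its nearest Phase II figure is the required sample size, which reproduces. For apixaban at HR 0.75, the events needed are (1.960 + 0.842)² / (0.393 × 0.607 × (ln 0.75)²) ≈ 398. Dividing the unrounded count by 0.0119 gives 33,408, against the stated 33,340 (0.2% apart). The formula has no covariate term, so this point leaves the sample size unchanged.

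**Possible size.** The documents give no prevalence by drug and no risk ratio (RR) for either variable. All such inputs below are assumptions. Each variable is treated as binary and independent of the measured covariates.

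- Standardised difference = |p_N − p_W| / √{[p_N(1 − p_N) + p_W(1 − p_W)] / 2}
- Factor on the HR = [1 + p_N(RR − 1)] / [1 + p_W(RR − 1)]

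Here p_N and p_W are the prevalences in NOAC and warfarin users.

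| Assumed case | p_N | p_W | Std. difference | RR | Factor on HR |
|---|---|---|---|---|---|
| No imbalance, either variable | equal | equal | 0 | any | 1.00 |
| Medical aid | 6% | 10% | 0.148 | 1.3 | 1.018/1.030 = 0.988 |
| Medical aid | 6% | 10% | 0.148 | 2.0 | 1.060/1.100 = 0.964 |
| Prior admission | 30% | 40% | 0.211 | 1.5 | 1.150/1.200 = 0.958 |
| Prior admission | 30% | 40% | 0.211 | 2.0 | 1.300/1.400 = 0.929 |
| Prior admission, reversed | 40% | 30% | 0.211 | 2.0 | 1.400/1.300 = 1.077 |

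Applied to the plan's edoxaban HR of 0.81, the factors 0.988 and 0.929 give 0.80 and 0.75, and the reversed case gives 0.87. A harsher case for admission (30% against 50%, RR 2.0) gives 1.300/1.500 = 0.867. Correlation with the listed covariates would be expected to pull these factors towards 1.

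**The case against.** A reader might infer that the plan excludes insurance type from the model, that the model cannot balance it, and that the hazard ratios are therefore biased in favour of the NOACs. The documents support none of these.

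- **Exclusion.** The sociodemographic sentence is open-ended. The Abstract's pair of age and sex cannot be a closed list, because it leaves out index year, which Protocol 9.3 includes. The row in the weighted tables may mean that insurance type was intended as a covariate. The table shells are weak evidence either way: they also carry follow-up time, which is not a baseline variable, and a 2012 index year, before cohort entry opens. For insurance type this is a mismatch between list and table, not a proven omission.
- **Cannot balance.** Weighting on age, comorbidity, medications and visits can balance a correlated variable in part. The model is simply not specified to balance it.
- **Bias towards the NOACs.** The admission-code requirement applies to every drug group alike. It makes admission-proneness a likely predictor of the outcome, but confounding also needs a link with drug choice, and the documents show none.

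It is also fair to say that Charlson and HAS-BLED scores, fracture and trauma capture part of recent serious illness, that active cancer is excluded from Phase II, that one sensitivity analysis drops patients with prior bleeding, and that Protocol 9.9 acknowledges residual confounding.

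Two things stand after this. Prior admissions are absent from every list and table, and insurance type has no stated place in the model although its balance will be displayed.

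**Conclusion.** The point holds as a specification gap that is cheap to close. The absence of an inpatient-use covariate is firm; for insurance type, the covariate lists and the balance tables need to be reconciled. Whether the hazard ratios would be confounded as a result cannot be settled from the documents. On moderate assumptions a single variable multiplies the HR by 1.00 to about 0.93, and the direction could reverse. That range rests wholly on assumed prevalences and risk ratios and on independence from the listed covariates, which is the least favourable assumption for the plan. Adding the two terms could reduce residual confounding; it cannot be said to remove it.

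**What to change.** In Protocol 9.3 and SAP 8.4, name these as propensity score terms:

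1. Health insurance type at index, with one set of categories used in Tables 1-4 (which now include Veterans) and Tables 13-16 (which do not).
2. Number of inpatient admissions, or inpatient days, in the 6 months ending the day before the index VTE encounter. This differs on purpose from the outpatient-visit window, which runs to the index date. Treatment may start up to 30 days after diagnosis, so a window ending at the index date would count the VTE admission itself.

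Add the admission variable to Tables 13-16 and apply the <0.1 criterion to both. A sentence on what is done when a covariate misses the criterion would also help.

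The cost is two more terms in a logistic model, drawn from data already held, with projected cohorts of 36,162 to 89,124 patients per comparison. The weights become slightly more variable, and both the protocol and the SAP need a short edit.
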